### 1.1. Study Rationale

The purpose of this study is to establish the safety and preliminary evidence of efficacy of namilumab in subjects who have active cardiac sarcoidosis (CS). If successful, the results will inform the design of a further clinical trials and registration of namilumab as the first novel therapy for sarcoidosis in decades and the first biologic option for this disease.

### 1.2. Background

Sarcoidosis is a multi-organ autoimmune disease characterized by the presence of non-necrotizing granulomas believed to be formed from an exaggerated immune response to as of yet unidentified antigens. Granulomas are tightly clustered formations of monocytes/macrophages and multinucleated giant cells (MGCs; fused activated macrophages) interspersed with CD4+ T cells. Normal granulomas contain central necrosis and form in response to foreign pathogens that cannot be eliminated. In contrast, sarcoid granulomas do not contain necrosis, and the cause of their formation is unknown.

The clinical course of sarcoidosis is highly heterogeneous, ranging from chest radiograph abnormalities discovered during routine screening of asymptomatic individuals to severe disease in patients with pulmonary fibrosis. Approximately 200,000 individuals are affected with sarcoidosis in the US (Baughman, 2016). About 25% to 33% of these patients have persistent granulomas and develop a chronic progressive disease that significantly impacts quality of life and causes increased morbidity and mortality (Broos, 2018; Spagnolo, 2018). Nearly all (~90%) patients experience pulmonary involvement, and respiratory failure is the most common cause of death for these patients (Spagnolo, 2018). Oral corticosteroids are the mainstay of therapy, and although patients with chronic disease may receive second-line immunosuppressive steroid-sparing agents, only 25% of patients achieve full weaning off OCS. Both OCS and ISTs often cause significant toxicities, including weight gain, osteoporosis, diabetes, hypertension, and opportunistic infections (Hu, 2017; Soto-Gomez, 2016; Khan, 2017). Given that no new therapy has been approved for sarcoidosis in decades, development of a new safe and effective steroid-sparing agent for this disease represents an area of significant unmet medical need.

[figure not shown]
Patients with CS have non-necrotizing granulomas affecting the heart and represent 5% of the total sarcoidosis population (approximately 10,000 people in the US). The clinical manifestations include conduction abnormalities, arrhythmias (ventricular tachycardia/ventricular fibrillation), congestive heart failure, and sudden death (Hulten, 2016). Sarcoid granulomas may involve any part of the heart, although the left ventricle is the most commonly affected chamber. Prognosis of CS is related to extent and site(s) of involvement. Most deaths are due to arrhythmia or conduction defects; progressive heart failure due to massive granulomatous infiltration of the myocardium accounts for at least 25% of deaths (Lynch, 2014).

In addition to immunosuppressive and steroid-sparing therapies, patients with CS are treated with guideline-directed medical therapies for electrophysiological and heart failure manifestations (Gilotra, 2020). Data on immunosuppressive management is largely extrapolated from non-CS literature and from limited retrospective cohorts of CS patients and the role of these agents needs to be further defined in efforts to decrease the morbidity associated with corticosteroids. (Gilotra, 2020). Many CS patients are already being treated for arrhythmia with a pacemaker or implantable cardioverter defibrillator (ICD).

Treatment with an anti-GM-CSF agent to impact the development of CS granulomas would aim to suppress inflammation, minimize recurrences, and decrease incidence of arrhythmias and the need for pacemakers. All second- and third-line therapies are not FDA approved for use in sarcoidosis, supporting the need for new therapies for use in this condition. GM-CSF, a pro-inflammatory cytokine and myeloid cell growth factor, is thought to play a key role in granuloma formation by stimulating activation of tissue-resident macrophages and mobilization of monocytes/macrophages from bone marrow to tissue (Iannuzzi, 2007). GM-CSF has been shown to be upregulated in lesioned tissues of subjects with many different autoimmune diseases, including sarcoidosis granulomas. Inhibition of the GM-CSF pathway via neutralizing antibodies has shown beneficial effects in animal models of multiple autoimmune conditions (Hamilton, 2020; Lang, 2020; Mehta, 2020). A Phase 2, randomized, placebo-controlled trial of an anti-GM-CSF mAb therapy in subjects with asthma demonstrated evidence of benefit in pre-specified subgroups, suggesting a role for GM-CSF in lung hyperinflammation (Molfino, 2016). More recently, treatment with mAbs against GM-CSF or GM-CSF receptor (GM-CSFR) yielded positive results in randomized, placebo-controlled trials of subjects with RA

(Hamilton, 2020), giant cell arteritis (Cid, 2020), and severe coronavirus disease 2019 (COVID-19) (Temesgen, 2021; Patel, 2021), solidifying the role of GM-CSF in aberrant immune responses. Given the importance of GM-CSF in autoimmunity and macrophage function, it is unsurprising that over the past 30 years, a multitude of human tissue and mouse model studies have shown that GM-CSF plays a key role in the formation of granulomas, including sarcoid granulomas.

GM-CSF is an important cytokine during multiple parts of the granulomatous response, including the fusion of macrophages into MGCs (Lemaire, 1996; Okamoto, 2003; Rangel, 2014), as well as the cross-talk between CD4+ T cells and myeloid cells (Zhang, 2013; Becher, 2016; Dougan, 2019). When overexpressed in rat lungs via adenovirus, GM-CSF caused aberrant granuloma development and pulmonary fibrosis (Xing, 1996a; Xing, 1996b). In mice, GM-CSF was required for normal granulomatous responses against tuberculosis (TB) as GM-CSF-/- mice quickly succumbed to infection (Gonzalez-Juarrero, 2005). Specific GM-CSF expression in either lung epithelial cells or T cells alone partially restored control of *Mycobacterium tuberculosis* infection in GM-CSF-/- mice (Gonzalez-Juarrero, 2005; Rothchild, 2017). Administration of anti-GM-CSF neutralizing antibody to mice after TB infection worsened granuloma integrity, promoted an anti-inflammatory cytokine and macrophage milieu, and impaired host bacterial control, leading to weight loss and deterioration (Benmerzoug, 2018). Corroborating these findings, Bryson et al., 2019, demonstrated that GM-CSF is a critical regulator of macrophage state during TB infection, whereby GM-CSF blockade made macrophages more permissive to TB growth and GM-CSF addition improved mycobacterial control (Bryson, 2019).

Tchernev, 2006

Multiple different groups have reported increased levels of GM-CSF in bronchoalveolar lavage fluid, lung tissue, eye fluid, and serum of sarcoidosis subjects, when compared to healthy controls (Hoshino, 1995; Ishioka, 1996; Prior, 1996; Crouser, 2009; Patterson, 2013; Abu El-Asrar, 2020). Inconsistent with these data, one study demonstrated no difference between serum GM-CSF in sarcoidosis subjects vs controls, whereas serum GM-CSF was elevated in idiopathic pulmonary fibrosis subjects (Ziora, 2015). Nevertheless, GM-CSF messenger ribonucleic acid (mRNA) levels in alveolar fluid of sarcoidosis subjects correlated with clinical severity (Itoh, 1990; Itoh, 1993), and alveolar macrophages within lesions of sarcoid subjects were shown to have increased GM-CSF secretion (Enthammer, 1993; Itoh, 1998; Oltmanns, 2003). In an in vitro model derived from peripheral blood mononuclear cells of sarcoidosis subjects, GM-CSF was upregulated during the formation of pathogenic granulomas (Crouser, 2017). Importantly, given that GM-CSF deficiency leads to pulmonary alveolar proteinosis (PAP), GM-CSF plays a particularly critical role in the maintenance and action of alveolar macrophages, which are known effector cells in sarcoid granuloma formation (Silva, 2013).

Taken together, GM-CSF is a key regulator of granulomatous responses, and significant evidence suggests that GM-CSF may drive sarcoid granuloma formation. Namilumab, an mAb that neutralizes GM-CSF, has the potential to improve organ function in CS by downregulating the granulomatous response that drives the disease.

### 1.3. Benefit-risk Assessment

The benefit-risk profile of namilumab is considered favorable for the evaluation of its potential to improve signs, symptoms, and health-related quality of life (HRQoL) in subjects with CS in this Phase 2 trial.

GM-CSF is required for the maintenance of alveolar macrophages which clear pulmonary surfactant. High levels of autoantibodies against GM-CSF may cause PAP, a rare lung disease characterized by accumulation of surfactant causing impaired gas exchange (Tazawa, 2019). A potential risk of GM-CSF inhibition with namilumab is the development of PAP. To date, no patient has developed PAP in any anti-GM-CSF or anti-GM-CSFR mAb published trial (Hamilton, 2020), including a long-term open-label extension (OLE) study with a median treatment duration of 2.5 years (Burmester, 2018). It has been hypothesized that PAP can develop only from profound and sustained GM-CSF neutralization by polyclonal autoantibodies (Lang, 2020). This hypothesis was based on experiments by Piccoli et al., 2015, who demonstrated in vivo and in vitro that individual antibodies only partially neutralized GM-CSF, while complete neutralization of GM-CSF could only be achieved with multiple non-cross-competing antibodies (Piccoli, 2015). Encouragingly, Campbell et al., 2016, showed that, while therapeutic-level intravenous (IV) doses of anti-GM-CSFR mAb affected systemic GM-CSF signaling, this dose level had no effect on cellular responses to GM-CSF in the lung, providing an alternative explanation for the lack of PAP observed in trials (Campbell, 2016). To date, no events pertaining to PAP have been reported in clinical trials with namilumab.

Because GM-CSF plays an important role in activating the immune system, another risk of namilumab administration is the increased chance for opportunistic infection. Indeed, high titers of autoantibodies against GM-CSF have been associated with infection (Rosen, 2013). Nevertheless, no anti-GM-CSF or anti-GM-CSFR trials have reported an increased infection risk

(Hamilton, 2020). Unlike trials of TNF-targeting agents, no increase in TB has been observed, despite GM-CSF's role in granuloma formation and TB protection in mice (Bryson, 2019; Hamilton, 2020). This benign safety profile has been corroborated in recently reported (not yet peer reviewed) trials of anti-GM-CSF mAbs for severe hospitalized COVID-19 subjects who were expected to be particularly susceptible to opportunistic infection (Patel, 2021; Temesgen, 2020). One suspected unexpected serious adverse reaction of bacterial pneumonia was reported in the COVID-19 Investigator-initiated study (CATALYST).

Another potential risk is the possibility of decreased neutrophil count/mild neutropenia. In the first-in-human (FIH) (M1-1188-001-EM) single dose escalation study of namilumab in healthy subjects (0.2 mg/kg to 8 mg/kg IV), a spontaneously reversible trend in decreased white blood cell (WBC) and absolute neutrophil count was observed in some subjects dosed with namilumab. The decrease in WBC was not clinically significant, and there was no dose-dependent pattern. Two subjects had clinically significant low neutrophil values during the trial: 1 subject on 0.5 mg/kg namilumab had a neutrophil count of  $1.0 \times 10^9/L$  on Day 8 and recovered without treatment by Day 15, and another subject on 3 mg/kg namilumab had a neutrophil count of  $1.1 \times 10^9/L$  on Day 29 and recovered spontaneously 4 days later. Both subjects recovered spontaneously without medical intervention. In the NEXUS study, neutrophil count, and WBC count decrease were recorded as drug related for 1 subject in the namilumab 80 mg treatment group and 1 subject in the namilumab 150 mg treatment group.

Neutralization of GM-CSF potentially may cause infection by depression of neutrophil and macrophage functions. The incidence of any severe and/or serious infection (with or without neutropenia) will be subject to ongoing pharmacovigilance (PV) monitoring in the clinical trial. To date, no serious adverse events (SAEs) of decreased neutrophil count and neutropenia have been reported with namilumab.

Namilumab has been studied in humans in doses ranging from 0.2 mg/kg to 8 mg/kg in Study M1 1188 001 EM; at 150 mg and 300 mg doses in Study M1 1188 002 EM (PRIORA) and Study MT 203 2004 (TELLUS); at 80 mg, 150 mg, and 300 mg in Study MT 203/CPH 001; at 20 mg, 80 mg, and 150 mg in Study M1 1188 202 (NEXUS); at 20 mg, 50 mg, 80 mg, 150 mg, and 300 mg in Study M1 1188 203 (NEPTUNE); at 150 mg in Study IZN 101 (NAMASTE); and at 150 mg in an Investigator-initiated trial (CATALYST). To date, 403 subjects or healthy volunteers have been enrolled into the clinical development program for namilumab, with 332 subjects estimated to have received namilumab. In addition, 57 subjects with COVID-19 were treated with a single dose of 150 mg namilumab in an Investigator-initiated trial in the UK known as the CATALYST study (n=55) or Investigator-sponsored compassionate use study (n=2). Overall, namilumab has been well tolerated with an acceptable safety profile for further development.

Based on the known data, the potential benefits of namilumab treatment outweigh the potential risks. Preclinical and human tissue studies have suggested that GM-CSF plays a key role in the formation of granulomas, including sarcoid granulomas. Positive clinical trials of anti-GM-CSF agents in RA, giant-cell arthritis, and COVID-19 have demonstrated a key role of GM-CSF as a driver of autoimmunity and hyperinflammation. The sarcoidosis subjects in this study will have relatively severe disease and may be receiving high doses of OCS or will have failed several agents. Current treatment strategies, including long-term use of OCS are associated with significant toxicities ([Khan, 2017](#)), and other treatment options for these subjects (cytotoxic agents and anti-TNF agents) have toxicity concerns of their own ([Callejas-Rubio et al, 2018](#)). Given that no new therapy has been approved for sarcoidosis in decades, namilumab may prove to be a useful treatment for these patients with limited options.

In summary, the anticipated potential risks include the occurrence of adverse reactions i.e., decreased neutrophil count/mild neutropenia, PAP, infection, and/or hypersensitivity reactions. No AEs suggestive of PAP, severe hypersensitivity, or severe neutropenia have been reported in the namilumab clinical program to date.

The following have been delineated as important identified risks:

- AST and/or ALT elevation.

The following have been delineated as important potential risks:

- Decreased neutrophil count/mild neutropenia;
- PAP;
- Hypersensitivity/allergic reactions (IgE-mediated; non-IgE-mediated);
- Infection.

Based on nonclinical studies and the available data from 8 completed clinical studies, the risks associated with exposure to namilumab are justified by the anticipated benefits that may be afforded. The benefit-risk ratio for namilumab is considered positive for the further study of namilumab in subjects with CS.

Identified potential risks and the planned mitigation strategies are described in [Table 1](#). More detailed information about the known and expected benefits and risks, reasonably expected AEs associated with namilumab, and mitigation strategies may be found in the Investigator's Brochure.

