### Phase 2 Liver Function Stopping Criteria and Follow-up Assessments

Liver Function Stopping Criteria	
ALT-absolute	ALT $\geq 5 \times$ ULN
ALT Increase	ALT $\geq 3 \times$ ULN persists for $\geq 4$ weeks
Bilirubin	ALT $\geq 3 \times$ ULN and bilirubin $\geq 2 \times$ ULN ( $>35\%$ direct bilirubin)
INR^2	ALT $\geq 3 \times$ ULN and international normalized ratio (INR) $>1.5$ , if INR measured
Cannot Monitor	ALT $\geq 3 \times$ ULN and cannot be monitored weekly for 4 weeks
Symptomatic	ALT $\geq 3 \times$ ULN associated with symptoms (new or worsening) believed to be related to liver injury or hypersensitivity

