### Actions and Follow-up Assessments following ANY Liver Function Event that Requires Study Treatment Discontinuation

Actions	Follow-up Assessments

• Immediately discontinue study treatment.

• Report the event to the Sponsor within 24 hours.

• Complete the liver event eCRF and complete an SAE data collection tool if the event also met the criteria for an SAE.

• Perform liver function follow-up assessments.

• Monitor the subject until liver function test abnormalities resolve, stabilize, or return to Baseline (see MONITORING).

• Do not restart/rechallenge subject with study treatment unless allowed per protocol and Sponsor Medical Governance approval is granted.

• If restart/rechallenge not granted, permanently discontinue study treatment and may continue subject in the study for any protocol specified follow up assessments.

	

• Viral hepatitis serology.

• Blood sample for PK analysis obtained after the most recent dose.

• Serum creatine phosphokinase and lactate dehydrogenase.

• Fractionate bilirubin if total bilirubin is <math>\geq 2 \times</math>ULN.

• Complete blood count with differential to assess eosinophilia.

• Record the appearance or worsening of clinical symptoms of liver injury, or hypersensitivity, on the AE report form.

• Record use of concomitant medications (including acetaminophen, herbal remedies, and other over-the-counter medications) on the concomitant medications report form.

• Record alcohol use on the liver event alcohol intake eCRF.

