MONITORING:  For bilirubin or INR criteria: Repeat liver function tests (include ALT, AST, ALP, bilirubin) and perform liver function follow-up assessments within 24 hours.  Monitor subject twice weekly until liver function test abnormalities resolve, stabilize or return to Baseline. A specialist or hepatology consultation is recommended.  For all other criteria: Repeat liver function tests (include ALT, AST, ALP, bilirubin) and perform liver function follow-up assessments within 24 to 72 hours.  Monitor subjects weekly until liver function abnormalities resolve, stabilize, or return to Baseline.	For bilirubin or INR criteria: Anti-nuclear antibody, anti-smooth muscle antibody, Type 1 anti-liver kidney microsomal antibodies, and quantitative total IgG or gamma globulins.  Serum acetaminophens adduct HPLC assay (quantifies potential acetaminophen contribution to liver injury in subjects with definite or likely acetaminophen use in the preceding week).  Liver imaging (ultrasound, magnetic resonance, or CT) and/or liver biopsy to evaluate liver disease; complete Liver Imaging and/or Liver Biopsy eCRFs.
---	--

1. Serum bilirubin fractionation should be performed if testing is available. If serum bilirubin fractionation is not immediately available, discontinue study treatment if ALT  $\geq 3 \times \text{ULN}$  and bilirubin  $\geq 2 \times \text{ULN}$ . Additionally, if serum bilirubin fractionation testing is unavailable, **record the absence/presence of detectable urinary bilirubin on dipstick** which is indicative of direct bilirubin elevations suggesting liver injury.
2. All events of ALT  $\geq 3 \times \text{ULN}$  and bilirubin  $\geq 2 \times \text{ULN}$  ( $> 35\%$  direct bilirubin) or ALT  $\geq 3 \times \text{ULN}$  and INR  $> 1.5$  may indicate severe liver injury (**possible 'Hy's Law'**) and **must be reported as an SAE (excluding studies of hepatic impairment or cirrhosis)**. The INR measurement is not required, and the stated threshold value will not apply to subjects receiving anticoagulants.
3. New or worsening symptoms believed to be related to liver injury (such as fatigue, nausea, vomiting, right upper quadrant pain or tenderness, or jaundice) or hypersensitivity (such as fever, rash, or eosinophilia).

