## Phase II Liver Function Increased Monitoring Criteria with Continued Therapy

Liver Function Increased Monitoring Criterion and Follow-up	
Criterion	Actions
ALT $\geq 3 \times \text{ULN}$ and $< 5 \times \text{ULN}$ and bilirubin $< 2 \times \text{ULN}$ , without symptoms believed to be related to liver injury or hypersensitivity, and who can be monitored weekly for 4 weeks	

Notify the Sponsor Medical Monitor within 24 hours of learning of the abnormality to discuss subject safety.

Subject can continue study treatment.

Subject must return weekly for repeat liver function tests (ALT, AST, ALP, bilirubin) until the abnormalities resolve, stabilize or return to Baseline.

If at any time, the subject meets liver function stopping criteria, proceed as previously described.

If, after 4 weeks of monitoring, ALT <math>< 3 \times \text{ULN}</math> and bilirubin <math>< 2 \times \text{ULN}</math>, monitor subjects twice monthly until liver function tests normalize or return to Baseline.

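### In the readable Appendix 7 rules, a possible Hy's Law case led by AST is not automatically an SAE and has no fixed 24-hour retest, although AST elevation is part of the only important identified risk

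*Combined protocol and SAP*

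**What the plan says.** Section 1.3 names one important identified risk: "AST and/or ALT elevation". Table 1 traces it to nonclinical work and five clinical studies, and lists exclusion criteria and routine pharmacovigilance as the response. Exclusion criterion 7 in Section 4.2 bars AST, ALT or ALP above 2×ULN at entry.

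Appendix 7 holds six stopping rows and one increased-monitoring row. Each is written on ALT; one reads "ALT $\geq 3 \times$ ULN and cannot be monitored weekly for 4 weeks". Note 2 takes the bilirubin and INR rows, calls them possible Hy's Law, and says such events "must be reported as an SAE (excluding studies of hepatic impairment or cirrhosis" and so on. It adds: "The INR measurement is not required, and the stated threshold value will not apply to subjects receiving anticoagulants". For these two rows the liver panel is repeated within 24 hours, and then: "Monitor subject twice weekly until liver function test abnormalities resolve, stabilize or return to Baseline". For the other stopping rows the interval is 24 to 72 hours, then weekly.

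The action table is headed "Actions and Follow-up Assessments following ANY Liver Function Event that Requires Study Treatment Discontinuation". Its follow-up list includes "Serum creatine phosphokinase and lactate dehydrogenase". The separate increased-monitoring table covers ALT from 3 to below 5×ULN with bilirubin below 2×ULN, and states: "Subject can continue study treatment". In Appendix 7, AST appears only among the tests to repeat.

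Section 4.4.2.4 has the Investigator consider stopping when a condition in Figure 2 is met or when it serves the subject, after discussion with the Sponsor.

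**The concern.** Note 2 treats a transaminase rise with raised direct bilirubin or INR as a possible sign of severe liver injury. It removes discretion: the event is reported as an SAE, which under Section 7.3.2 means within 24 hours, and the panel is repeated within 24 hours. Those safeguards depend on ALT alone, while the risk they serve is stated for either enzyme. The same pattern with AST as the leading enzyme triggers neither duty in the readable text.

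What is at stake is prompt, uniform handling of a rare but serious presentation in individual subjects. No safety endpoint is lost, because AST is in the chemistry panel (Appendix 5) and reaches the laboratory and AE summaries in Section 8.6.

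**Working it through.** This is a check of logical conditions and visit dates. The plan states no figure to reproduce.

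**1. Do the rules respond to AST?** Inputs are the Appendix 7 stopping rows, the increased-monitoring row and note 2. All values are multiples of ULN, with direct bilirubin above 35%. The two profiles are illustrative and mirror each other.

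| Appendix 7 rule | Condition | AST 8, ALT 2.5, bilirubin 2.5 | ALT 8, AST 2.5, bilirubin 2.5 | First profile, with ALT or AST in the bilirubin and INR rules |
|---|---|---|---|---|
| ALT-absolute | ALT ≥5 | no | yes | no |
| ALT increase | ALT ≥3 for ≥4 weeks | no | depends on duration | no |
| Bilirubin | ALT ≥3 and bilirubin ≥2 | no | **yes** | **yes** |
| INR | ALT ≥3 and INR >1.5, if measured | no | if INR >1.5 | if INR >1.5 |
| Cannot monitor | ALT ≥3, no weekly monitoring | no | depends | no |
| Symptomatic | ALT ≥3 with symptoms | no | depends | no |
| Increased monitoring | ALT ≥3 and <5, bilirubin <2, no symptoms, can be monitored weekly | no | no | no |
| Note 2 (mandatory SAE) | bilirubin or INR row | no | **yes** | **yes** |

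All 7 criteria (6 + 1) need ALT ≥3×ULN, so the AST-led profile meets 0 of 7 and note 2 is not met. Note 2 is a reporting rule on two of the seven, not an eighth criterion. This follows from the wording: any profile with ALT below 3×ULN gives 0 of 7, whatever the AST, bilirubin or INR.

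**2. What covers the AST-led case instead?**

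- Section 7.2.8: the Investigator must review the laboratory report and document the review. Clinically significant changes are recorded as AEs, and clinically significant values should be repeated. No interval is given.
- Appendix 3: an important medical event is itself an SAE criterion, and events that may jeopardize the subject are normally to be classed as serious. Both turn on medical judgement.
- Sections 4.4.2.2 and 4.4.2.4: study drug may be held or stopped at discretion.
- Appendix 7 action table: its heading can be read to cover a discretionary stop. The 24-hour repeat, however, is tied to the bilirubin and INR criteria, which this case does not meet.

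**3. Outer bound on delay if nobody acts.** Chemistry days from Appendix 1 after the Week 2 visit: 15, 43, 71, 99, 127, 155, 183, 211, 238.

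- Gaps: 43 − 15 = 28, and likewise for seven gaps; then 238 − 211 = 27. Total 8 gaps.
- With ±3-day windows at both ends: 28 + 3 + 3 = 34 days at most.
- Five of the 8 gaps contain weekly remote contacts (Weeks 3–5, 7–9, 11–13, 15–17 and 19–21), with AE questions but no blood draw. The other three (Weeks 22 to 34) contain none.

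The comparison is 24 hours under the existing bilirubin and INR schedule.

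**The case against.** The strongest reply is that the general safety net already reaches this case. An AST of 8×ULN with bilirubin of 2.5×ULN would be seen at the required laboratory review and would very likely be judged clinically significant. Appendix 3 leans towards calling it serious, and Section 7.3.2 then requires reporting within 24 hours. The DMC also reviews unblinded safety data (Section 8.9). Most of this stands. A reader might infer that an AST-led case would go unreported or untested for four to five weeks. The documents do not support that: such a gap needs the Investigator to dismiss a grossly abnormal result already reviewed. What remains is that the protocol does not leave the ALT-led twin to judgement and gives no reason for the difference.

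Second, ALT-only rules may be deliberate. AST can come from heart or muscle, and this is a cardiac population. That is a good argument against acting on isolated AST elevation. It is weaker when direct bilirubin or INR is raised too, and the creatine phosphokinase test already listed helps to sort such cases.

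Third, Figure 2 may include AST. It is the algorithm that Section 4.4.2.4 cites for stopping, so nobody should conclude from Appendix 7 alone that the whole liver plan ignores AST. The SAE duty and the retest intervals, though, sit in the Appendix 7 text.

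Fourth, Section 4.4.2.4 presents the Appendix 7 actions as suggestions. Note 2 is nevertheless worded as an obligation.

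**Conclusion.** The point holds in a narrow form. In the readable Appendix 7 text, an AST-led case (AST ≥3×ULN, ALT <3×ULN, with bilirubin ≥2×ULN and over 35% direct, or INR >1.5) meets 0 of 7 numeric criteria. It is not automatically an SAE and has no set 24-hour retest. It rests on judgement, which the protocol steers towards action; 28 to 34 days is the outer bound if that judgement fails, not the expected delay.

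A reader might also infer that the protocol contradicts itself. It does not: Table 1 promises exclusion criteria and routine pharmacovigilance for this risk, both are present, and no AST threshold is promised. An AST-led case that met a general seriousness criterion, such as hospitalization, would be an SAE in any event.

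The conclusion assumes that Figure 2 does not itself impose these duties on AST. The change is worth recommending: it closes a gap in a mandatory safeguard for the one identified risk at little cost.

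**What to change.** In Appendix 7, replace *ALT ≥3×ULN* with *ALT or AST ≥3×ULN* in four places: the bilirubin stopping row, the INR stopping row, note 1, and both limbs of note 2. Keep the condition of more than 35% direct bilirubin and the anticoagulant exemption. Changing the rows together with the notes means no separate pathway is needed. The existing actions, 24-hour repeat, twice-weekly monitoring, liver-event eCRF and creatine phosphokinase test then apply as written. Discontinuation stays subject to Section 4.4.2.4. Make Figure 2 consistent if it is also ALT-only. Leave isolated AST elevation with normal bilirubin and INR unchanged; whether to act on it is a trade-off for the sponsor's hepatic safety experts.

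Cost:

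- **Amendment:** a short change to Appendix 7 with IRB approval (Appendix 6), and a laboratory alert. AST and total and direct bilirubin are already in the panel drawn at 11 timepoints; INR stays optional.
- **Per event:** if it lasts 28 days, 1 + 2 × 4 = 9 liver panels. At the full 16.5 mL safety draw (Table 6), 9 × 16.5 = 148.5 mL; a liver-only draw would need less. This is sizeable against the roughly 250 mL study maximum in Section 7.2.11, but that section allows repeat samples for safety. One set of follow-up tests is added.
- **Extra SAE reports:** the frequency is not in the documents. Assuming, purely for illustration, that 0.5% to 5% of subjects have such an event, 30 × 0.005 = 0.15 to 30 × 0.05 = 1.5 reports. Some will prove to be AST of cardiac or muscle origin.
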